2.3. Co-Production of CoCoA-PAD

The CoCoA-PAD assessment battery, and indeed all aspects of this research study, have been developed using a coproduction methodology, as outlined by the NIHR ([NIHR Guidance on co-producing a research project](#)). The co-production group consists of five older adults (including two with neurological conditions, one from an ethnic minority background, and one with educational deprivation), five assistant psychologists, two memory nurses, and seven clinical psychologists and neuropsychologists. The older adult coproduction group are involved in ensuring the assessment is well tolerated, the instructions are clear, that the test does not unduly discriminate against people with low computer literacy. The assistant psychologist group are involved in coproducing the usability of the assessment for the examiner. The memory nurses are coproducing the clinical observation checklists. The clinical psychologist and neuropsychology group are involved in coproducing the assessment governance and training requirements. All aspects of the assessment have been or are currently being co-produced.

CoCoA-PAD is delivered using Gorilla Experiment Builder 2.0 (EB2). Approximately half of the subtests (COBALT, MANE, SILT, Verbal Fluency, Connected Speech, Clock Drawing, and ALF) were initially developed and coproduced using a CoCoA-PAD web-based app, but due to costs associated with data storage, these tasks were transferred directly into Gorilla EB2. The remaining subtests were designed and co-produced using Gorilla EB2, an online platform for designing and running behavioural experiments. Gorilla Experiment Builder provides precise stimulus delivery, secure data collection, and easy remote access, making it well-suited for this research.

[figure not shown]

Figure 1. Proposed hierarchical structure of CoCoA-PAD

[figure not shown]

Figure 2. Mapping of CoCoA-PAD subtests onto the preclinical AD syndrome, and the four prodromal AD syndromes.

3. Objectives

3.1. Primary objective:

The long-term aim of this research is to develop a cognitive assessment which can be implemented into memory services and provides clinically meaningful information for healthcare staff. There are four primary research objectives, which stem from this ambition:

- i. To establish the diagnostic accuracy of the CoCoA-PAD subtests at distinguishing people with preclinical Alzheimer's disease (stages 1 and 2) from healthy controls.

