11.3. Sample Size

Given that there are three independent studies, a justification of the proposed sample is outlined for each study.

Study 1: Diagnostic Accuracy of CoCoA-PAD Subtests

The aim of this study is to test whether CoCoA-PAD subtests can distinguish between healthy controls (i.e., people with subjective memory problems without any evidence of AD biomarkers or cognitive decline) and people with preclinical and prodromal Alzheimer's disease. This study uses a prospective research design, and therefore exact participant numbers in each diagnostic criteria cannot be determined until after data collection. Figure 3 provides an estimate of the final sample composition, which includes of 36 healthy controls, 18 people with preclinical AD, and 40 people with prodromal AD. A power calculation using a fixed one-way ANOVA (estimated effect size $f = 0.33$ (moderate effect), $k = 3$) required a minimum sample of 90 to achieve the required power ($\alpha = 0.05$, $1-\beta = 0.8$). Based on current projections (36 controls, 18 preclinical AD, and 40 with prodromal AD), this would be achieved.

Study 2: The relationship between CoCoA-PAD subtests and the health of key brain regions

This study aimed to measure the strength of the association between key brain regions and performance on CoCoA-PAD subtests. It includes a subgroup of study 1 participants. A power calculation using a linear multiple regression (fixed model, single regression coefficient, effect size f^2 (0.1, small) required a minimum sample of 64 participants to achieve the required power ($\alpha = 0.05$, $1-\beta = 0.8$).

Study 3: Testing whether CoCoA-PAD is sensitive to pathological cognitive decline in AD

This study aimed to compare 1 year change score (time 2 score – time 1 score) on CoCoA-PAD subtest scores in people with early Alzheimer’s disease and healthy controls. It includes a subgroup of study 1 participants. A power calculation using a matched pairs *t* test (Cohen’s *d* = 0.5 (moderate)) required a sample of 27 to achieve the required power ($\alpha = 0.05$, $1-\beta = 0.8$).

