11.4. Provisional Data Analysis

The CI will work with a medical statistician, [name], to finalise the data analysis plan, and will publish this on Open Science Framework, prior to the start of data collection. This will ensure both rigour and transparency. A provisional data analysis plan is outlined for each sub-study below. Furthermore, Appendix 2 provides a specific breakdown of the hypotheses and analysis plan for each CoCoA-PAD subtest. This should be considered provisional and may be subject to change prior to the start of the study.

Study 1: Diagnostic Accuracy of CoCoA-PAD Subtests

The aim of this study is to test whether each CoCoA-PAD subtest can distinguish between healthy controls and people with preclinical and prodromal Alzheimer’s disease. This study will use a Welch’s ANOVA to accommodate unequal variances and sample sizes ($k=3$, healthy controls, preclinical AD, and prodromal AD) and Games–Howell post hoc test. A series of receiver operator curves, area under the curves, and optimised sensitivity and specificity values based on Youden index, will be calculated to measure the diagnostic accuracy of each subtest also.

Study 2: The relationship between CoCoA-PAD subtests and the health of key brain regions

Associations between CoCoA-PAD subtest scores and regional brain volume, density and connectivity will first be explored using Spearman correlations, adjusted for false discovery rate using the Benjamini-Hochberg Procedure. Multiple linear regression models will then be used to assess the predictive value of MRI-derived volumetric measures on CoCoA-PAD performance, adjusting for potential confounders including age, sex, education, and intracranial volume. Model fit and assumptions will be evaluated to ensure robustness.

Study 3: Testing whether CoCoA-PAD is sensitive to pathological cognitive decline in AD

Change scores on CoCoA-PAD subtests will be calculated by subtracting time 1 score from time 2 score. As such, negative change scores will denote a decline in performance. A series of *t* tests will be used to test whether the prodromal AD group exhibit higher levels of cognitive decline over a one-year interval. To control for the false discovery rate (FDR) across multiple *t*-tests, the Benjamini–Hochberg procedure was applied with a threshold of $q = 0.05$. This method adjusts *p*-values to reduce the risk of Type I error when conducting multiple comparisons.

Data Analysis Software

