COBALT (Colour and Object Binding and Localising Test)

- Cognitive Theory: Tests conjunctive binding (colour, form, spatial localisation); requires parietal–temporal–entorhinal integration.
- Diagnostic Hypothesis: Distinguishes preclinical vs healthy, and prodromal vs healthy.

- Neuroimaging Hypotheses:
 - DTI tracts: superior longitudinal fasciculus; vertical occipital fasciculus; inferior longitudinal fasciculus; uncinate fasciculus (for EC).
 - NODDI regions: entorhinal cortex; posterior parietal cortex (intraparietal sulcus, angular gyrus); precuneus; perirhinal cortex; occipital cortex.
 - T1 (secondary): parietal & occipital cortical thickness.

ALF (Accelerated Long-Term Forgetting)

- Cognitive Theory: Tests delayed memory attrition; hippocampal-dependent consolidation.
 - Diagnostic Hypothesis: Distinguishes prodromal vs healthy (less sensitive in preclinical).
 - Neuroimaging Hypotheses:
 - DTI tracts: fornix; parahippocampal cingulum; uncinate fasciculus.
 - NODDI regions: entorhinal cortex; hippocampus; anterior temporal cortex.
 - T1 (secondary): hippocampal subfield volume.
-

SPATIAL PROCESSING

TASP (Test of Allocentric Spatial Processing)

- Cognitive Theory: Tests allocentric navigation; hippocampal–parietal–precuneus integration.
- Diagnostic Hypothesis: Distinguishes preclinical vs healthy, and prodromal vs healthy.
- Neuroimaging Hypotheses:
 - DTI tracts: fornix; parahippocampal/posterior cingulum; superior longitudinal fasciculus.
 - NODDI regions: entorhinal cortex; hippocampus; precuneus; retrosplenial cortex; posterior parietal cortex.
 - T1 (secondary): hippocampal & precuneus volume.

Clock Drawing Test

- Cognitive Theory: Tests visuoconstruction and executive control; parieto-frontal integration.
 - Diagnostic Hypothesis: Distinguishes prodromal vs healthy.
 - Neuroimaging Hypotheses:
 - DTI tracts: superior longitudinal fasciculus; inferior fronto-occipital fasciculus.
 - NODDI regions: entorhinal cortex; posterior parietal cortex; dorsolateral prefrontal cortex.
 - T1 (secondary): parietal cortical thickness.
-

PERCEPTUAL DISCRIMINABILITY

Motion Perception Test

- Cognitive Theory: Tests dorsal-stream integration of motion and form; occipital–parietal–entorhinal.
- Diagnostic Hypothesis: Distinguishes preclinical vs healthy.
- Neuroimaging Hypotheses:
 - DTI tracts: optic radiations; vertical occipital fasciculus; superior longitudinal fasciculus.

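### Study 1 tests all three group pairs with single-step Games–Howell although every stated hypothesis is a comparison with controls: valid, but it gives up as much as about 13 points of power per subtest

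*Protocol*

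**What the plan says.** Section 11.4 (Study 1) plans, for each subtest, a Welch "ANOVA to accommodate unequal variances and sample sizes" over three groups with a Games–Howell post hoc test; the groups and the test are named together as "healthy controls, preclinical AD, and prodromal AD) and Games"–Howell. ROC curves, AUCs and Youden-based sensitivity and specificity are planned alongside. The section does not say whether Games–Howell is run only after a significant omnibus test.

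Section 3.1 gives primary objective i as "distinguishing people with preclinical Alzheimer's disease (stages 1 and 2) from healthy controls". Objective ii is the same for prodromal AD, again against healthy controls. Appendix 2 gives a diagnostic hypothesis per subtest, for example for Clock Drawing "Diagnostic Hypothesis: Distinguishes prodromal vs healthy". Section 11.3 sizes Study 1 on a one-way ANOVA with f = 0.33 and three groups, and projects "36 healthy controls, 18 people with preclinical AD, and 40 people with prodromal AD". Section 4.6 promises false discovery rate adjustment for multiple comparisons. Section 11.4 calls the plan provisional.

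**The concern.** Games–Howell protects three pairwise comparisons in one step. The protocol's objectives and hypotheses need at most two of them, and for many subtests only one. The contrasts that answer objectives i and ii are therefore held to a stricter threshold than 5% within-subtest error control requires. Section 11.3 powers only the omnibus test, so these contrasts have no planned reserve, and objective i rests on about 18 preclinical cases. What is at stake is the chance of detecting a real difference from controls in the group-comparison part of Study 1.

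**Working it through.** **Contrasts in Appendix 2.** Five subtests name both control contrasts (SILT, MANE, COBALT, TASP, Central Auditory Processing). Seven name one: Motion Perception (preclinical), and ALF, Clock Drawing, Odd-One-Out, Overlapping Objects, Verbal Fluency and Antisaccade (prodromal). Preclinical v controls: 5 + 1 = 6. Prodromal v controls: 5 + 6 = 11. Total 17. Preclinical v prodromal: 0.

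**The plan's own figure.** Noncentral F with λ = N·f² and df (2, N − 3) gives power 0.793 at N = 90, reaches 0.80 at N = 92, and is 0.811 at the projected N = 94. The stated minimum of 90 reproduces to within two participants.

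**Threshold.** Games–Howell rejects a pair when |t| > q(0.95; 3, ν)/√2, with ν the Welch degrees of freedom. That is a two-sided level of about 0.0195 per pair.

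**Mean patterns.** With SD 1 and weights n/N, f² = Σ(n_j/N)(μ_j − μ̄)². If both AD groups differ from controls by d, then f = d·√[(36/94)(58/94)] = 0.486d, so f = 0.33 gives d = 0.679. The other patterns are scaled in the same way.

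**Power.** Simulated at 36/18/40 with normal scores, equal SDs and two-sided tests. Planned means Welch ANOVA at 0.05, then Games–Howell. Closed means the same ANOVA, then unadjusted Welch t tests at 0.05.

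| Means (control, preclinical, prodromal) | Contrast with controls | Planned | Closed |
|---|---|---|---|
| 0, 0.679, 0.679 | preclinical | 47% | 60% |
| | prodromal | 70% | 76% (Holm 78%) |
| 0, 0.367, 0.735 | preclinical | 13% | 23% |
| | prodromal | 77% | 79% |
| 0, 0.839, 0 | preclinical | 67% | 74% |
| 0, 0, 0.667 | prodromal | 68% | 75% |

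In the first pattern Holm over the two control contrasts also gives 60% for preclinical. Over all patterns tried at f = 0.33, the largest gain from Holm or the closed test was 13.6–13.7 points for preclinical (means 0, 0.63, 0.70: 40.5% v about 54%) and about 12 for prodromal. Against single-step Bonferroni for two contrasts, the largest gain was 4–5 points.

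**Error control.** When one AD group truly differs and the other does not, the null control comparison is rejected about 2% of the time as planned and 5% under Holm or the closed test. With no effects at all, the chance of any false positive on the two control contrasts is 3.3% as planned, 4.2% closed and 4.8% Holm.

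**Where the loss comes from.** The omnibus gate on top of Games–Howell costs 0–2 points. Covering three pairs rather than two costs about 2–4. The remainder, up to about 9, is single-step against step-down or closed testing.

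**Single-contrast subtests.** No within-subtest correction is needed here. In the last pattern a single Welch t test at 0.05 has 81.8%, against 68.5% as planned: a difference of 13.3 points. Keeping an omnibus gate before that test costs about 6–9 points (for example 75.0% v 81.7%, and 79.1% v 88.5% in the second pattern).

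**The case against.** Games–Howell is a standard companion to Welch's ANOVA under unequal variances and group sizes, which is the reason section 11.4 gives. It is valid, and the plan is provisional. Section 4.1 lists the three categories against one another in general terms, and Appendix 2 expects ALF to be less sensitive in preclinical disease, so an all-pairs test is not foreign to the protocol. This stands: nothing here is an error or a contradiction. It does not supply an objective or hypothesis for preclinical v prodromal.

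A reader might infer that the plan loses power because it corrects twice, through the omnibus test and again through Games–Howell. The documents do not state a gate, and if there is one it explains at most about 2 points. A reader might also infer that sensitive subtests would be discarded as a result. Section 7.8 says insensitive tests will be removed but does not tie removal to this test, and the planned measures of diagnostic accuracy are the ROC/AUC results, which the choice of post hoc test does not touch. Nor does section 3.1 rank objective i above the other three.

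Finally, the power figures are per subtest and ignore the false discovery rate adjustment of section 4.6. That also stands: they compare within-subtest procedures and do not give the power of the whole multi-subtest analysis.

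**Conclusion.** The post hoc procedure is valid but less efficient than the stated hypotheses allow. At the protocol's projected group sizes and effect size, the loss per subtest is about 13 points at most against Holm, a closed test or, where one contrast is named, a single Welch t test. It is smaller under most mean patterns, and 4–5 points at most against Bonferroni for two. The figures assume two-sided tests, normal scores and equal SDs; with SD ratios of 1.5 the loss against Holm was 7–12 points. This is a cheap improvement to a provisional plan, not a correction of a validity error.

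**What to change.** In section 11.4, Study 1, replace Games–Howell with Welch t tests of only the control contrasts that Appendix 2 names for each subtest.

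- One named contrast (seven subtests): a single Welch t test at 0.05, with no omnibus gate.
- Two named contrasts (five subtests): Holm over the two. Alternatively, a Welch ANOVA at 0.05 followed by unadjusted Welch t tests, which is a closed procedure for three groups.
- State that the false discovery rate adjustment promised in section 4.6 is applied across the named contrasts, and which p values enter it.
- Report preclinical v prodromal with a confidence interval, as descriptive.

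The cost is a few sentences in the analysis plan and no extra data. Biomarker status is determined only after the Study 1 and 2 samples are collected (sections 4.6 and 8.10), so a documented change before then is made without knowledge of group membership. The downside is that there is no formal preclinical v prodromal test, for which the protocol has no objective or hypothesis.

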4.1. Study 1. Evaluating the Diagnostic Accuracy of CoCoA-PAD subtests

Participants

A total of 120 participants will be recruited: 60 participants with subjective cognitive decline (SCD) and 60 participants with mild cognitive impairment (MCI). Participants will be classified post-recruitment into four distinct diagnostic groups: healthy controls, preclinical AD, prodromal AD, and non-AD related MCI. Figure 3 provides a flow of the estimated frequencies of each diagnostic group within the sample.

Sampling

This study will use a stratified sampling approach with post-hoc diagnostic classification. A prospective quasi-experimental between-group research design will be employed.

A stratified sampling approach will ensure that key demographic information, including years of education and ethnicity, will match national population demographics of the UK. 2021 census data revealed that 6% of 70–74-year-olds in the UK are from non-white ethnic minority backgrounds. However, given that people from minority ethnic backgrounds are significantly more likely to have dementia but less likely to receive a diagnosis (Okeoghene Ighomereho, 2025), for the purpose of this study, the stratified sampling target will be inflated to 10%.

Similarly, 2021 census data has mapped the educational attainment of the UK population. No age-specific education attainment values were published, but regional values have been published, and Plymouth demographics have been selected for this study. This is based on coastal communities having higher rates of dementia, lower rates of diagnosis, and significant social inequalities which often exclude them from research (Alzheimer’s Research UK, 2024). This study will replicate educational attainment values, with provision for 5% variation in the recruitment to each education level – see Table 1.

Table 1. Educational Attainment and Stratified Sampling Target

Educational Attainment	Plymouth Demographics	CoCoA-PAD Recruitment Target Range
No Qualification	17%	14-26
Level 1 (O level any grade)	10%	6-18
Level 2 (O levels passes)	14%	11-23
Apprenticeship	6%	1-13
Level 3 (A level equivalent)	17%	14-26
Level 4 (3 rd level qualifications)	34%	35-47
Other	2%	0-8

Procedure

Participants will be recruited and classified post-recruitment into diagnostic groups on the basis of AD biomarker results (pTau-217) and performance on the M-ACE, using a cut-off score of 20 for MCI (Potts et al., 2022).

Measures

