strategies to support cognitive wellbeing. All feedback will be delivered in a sensitive, person-centred manner, and with a written feedback summary. Participants will be provided with information about the referral route for a memory assessment, should they wish to undergo a clinically assessment with a memory service.

This feedback will be primarily provided by the Chief Investigator, a qualified clinical neuropsychologist with substantial experience in cognitive assessment and communicating results to patients and their families. For sites outside of the primary research centre, feedback will either be delivered directly by the Chief Investigator or by a local research nurses trained and supervised by the Chief Investigator.

This approach reflects ethical guidance that supports sharing clinically meaningful information with participants when it is generated using validated tools, has clear interpretive value, and can support health literacy and informed decision-making.

CoCoA-PAD Disclosure

The study also includes novel digital cognitive assessments developed under the CoCoA-PAD protocol. These assessments are research tools under development and currently lack an any normative data or diagnostic benchmarks to interpret results in individual participants. Without reference values or validated clinical thresholds, it is not possible to determine what constitutes 'normal' or 'impaired' performance in the older adult population. Therefore, results from these digital cognitive tasks will not be disclosed to participants, as doing so would be speculative.

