7.8. Development of a Medical Device

The long-term ambition of CoCoA-PAD is to validate the cognitive assessments and then work towards achieving NICE registration as a tier 3 digital health technology to 'inform clinical management'. Subsequent research will therefore require MHRA approval.

Having reviewed the UKMDR2002 flowchart for MHRA approval ([flowchart Cls - Studies under UKMDR2002 v1 A4.pdf](#)), this study does not require MHRA approval for the following reasons:

- All the CoCoA-PAD cognitive tests are novel and have not been previously validated. Therefore, the CoCoA-PAD assessment battery is currently experimental.
- Depending on the results of this study, the CoCoA-PAD assessment will be altered, i.e., insensitive tests will be removed from the assessment to reduce time. Therefore, the assessment battery is not yet finalised.
- The CoCoA-PAD tests are not being used for a medical purpose in this study. Participants' results will not be used for classification purposes, and participants will not receive any feedback on the CoCoA-PAD performance, because this data is currently uninterpretable.
- The data from the CoCoA-PAD tests are not being used to develop another medical device.

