9.3. Data Collection and Processing

The CoCoA-PAD study will involve the collection and processing of a broad range of participant data.

Identifiable personal data

Identifiable personal information will include participants' full names, dates of birth, addresses, general practitioner (GP), and contact details. These identifiers are required for correspondence, safeguarding, and follow-up purposes. This data will be collected at the screening assessment and will be added to a REDCap database that is stored securely and separately from the primary research database. Researchers at the Devon and North East

London sites will have data entry and export permissions on REDCap to upload their participant information data.

Audio Recordings

Although our audio recordings will exclude direct identifiers (e.g. full name, date of birth, NHS number, address), a participant's voice is personal data under the UK GDPR/DPA 2018 because it could indirectly identify an individual. We will not process voices for the purpose of uniquely identifying participants (no voice-print recognition), so the audio is not treated as special-category biometric data under UK GDPR Article 9.

Audio recordings are required to develop speech-based biomarkers for Alzheimer's disease. The research appointment will be recorded, and therefore each participant will provide up to two hours of audio to enable reliable natural language processing and acoustic feature extraction, which in turn supports accurate digital biomarker development. Although a large sample is required, data minimisation is applied: only research-relevant material is recorded, inadvertent identifiers will be redacted during transcription, and access is strictly role-based. Audio is captured on institutionally managed devices via institutional Microsoft Teams accounts (with MFA and SharePoint sync), encrypted at rest and in transit. The University of Birmingham acts as a Data Processor under a formal Article 28 agreement, and analysis is conducted by [name] as an employee of that organisation.

Specific audio data collection procedures are in place for each research site:

- North East London NHS Foundation Trust (NELFT) research team will record sessions on NHS-managed laptops using the Trust's institutional Microsoft Teams accounts (MFA enabled), with automatic syncing to SharePoint.

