The MS SharePoint audio data folder will have access-controlled sharing. This data will only be available to the CI, [name], [name], [name], [name], and [name]. The audio data will be accessed by [name], at the University of Birmingham, who are listed as a Data Processor. Given the need complexity of this analysis and the need for multiple analysis pipelines, proportional data minimisation processes will be completed, as outlined previously, and [name] will have access to the raw audio recording files. Audio data will be uploaded to a locally downloaded and run version of Whisper, OpenAI, transcription service. When run locally on a computer, Whisper AI does not upload any data onto a server, and it is GDPR compliant. A transcript of the research session will be produced. Similarly, the audio file will be analysed using code that has been fully developed by [name]. Different types of acoustic and linguistic features will be extracted using Python code that is run locally - the data will not be uploaded to any third-party server at any point. Using those extracted features, a neural network classifier will be trained. The outcome of this classifier will be manually added to the REDCap database.

Demographic and Health Information

Participant demographic and health information will be collected using the Questionnaire feature of Gorilla Experiment Builder. The research sites will be provided with a survey link, with which they can administer the questionnaires and demographic survey to participants. Demographic variables collected will include participants' years of education, socioeconomic status, and relevant health history. Clinical self-report data will be gathered using standardised screening instruments for mood, sleep, and pain.

Gorilla Experiment Builder stores raw data on secure servers, which are only accessible to the primary researcher using their unique multi-factor log-in details. Therefore, only the CI will have access to this data, irrespective of where it was collected. No direct identifiers are stored in Gorilla, and therefore the data are pseudonymised. Raw data will be downloaded onto a Microsoft Excel spreadsheet and manually extracted and transferred into the primary research database on REDCap.

Neuropsychological Assessment Data

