In the CoCoA-PAD study, most raw assessment data is automatically within the secure Microsoft Azure environment using embedded analysis pipelines. Outputs from these automated processes are scored within Azure and can be extracted directly through Gorilla's data access platform. Some assessments, however, are not automatically scored and are therefore exported in their raw format. This includes audio recordings, clock drawings, and verbal fluency tasks. These raw files are placed into separate, access-controlled folders in the University of Plymouth SharePoint site file. Authorised researchers at the University of Birmingham (for audio analysis) and Sheffield Hallam University (for clock drawing and verbal fluency analysis) are granted access to these folders. They conduct their analyses, generate derived scores, and return these results to update the research database. Following completion of analysis, both institutions confirm in writing that all working copies of raw data have been deleted at or before study close. Full details of these processes are set out in the Data Management Plan.

- **University of Birmingham (UBham)** will act as a Data Processor for secondary analysis of exported audio recordings and related transcripts and anonymised MRI scans. UBham receives only pseudonymised audio and associated technical metadata (for example, timestamps, task identifiers) via the UoP SharePoint environment. UBham processes these data strictly on the documented instructions of the Controllers, co-ordinated by UoP as lead Controller, and returns only derived speech features to the Controllers. UBham does not receive linkage files or direct participant identifiers.

- **Sheffield Hallam University (SHU)** will act as a Data Processor for secondary analysis of anonymised clock drawings and verbal fluency data. SHU receives only exported clock drawings in raw image format and verbal fluency outputs in raw score format, all pseudonymised and containing no direct identifiers. SHU applies machine-learning and feature extraction methods to generate derived measures, which are returned to the Controllers. SHU processes data strictly on the documented instructions of the Controllers, co-ordinated by UoP as lead Controller, and does not receive linkage files or direct identifiers.

Both institutions act strictly under formal Controller–Processor agreements in accordance with Article 28 of the UK GDPR.

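### Youden-optimised sensitivity and specificity are chosen and evaluated on the same participants, so they will overstate each subtest's accuracy

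*Protocol*

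**What the plan says.** Diagnostic accuracy against healthy controls is the subject of primary objectives i (preclinical) and ii (prodromal) in section 3.1. For Study 1, section 11.4 names a Welch ANOVA, ROC curves and AUCs, and then states that "optimised sensitivity and specificity values based on Youden index, will be calculated to measure the diagnostic accuracy of each subtest also".

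There is one sample. Section 4.1 says "A total of 120 participants will be recruited", and section 11.3 expects this to yield "36 healthy controls, 18 people with preclinical AD, and 40 people with prodromal AD". No cut-off can be brought in from elsewhere. Section 7.7 says of the new tests: "Without reference values or validated clinical thresholds, it is not possible to determine what constitutes 'normal' or 'impaired' performance".

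Three scores involve machine learning:
- **Speech** (section 9.3, Audio Recordings): "Using those extracted features, a neural network classifier will be trained. The outcome of this classifier will be manually added to the REDCap database". On the audio itself, the same section says "The research appointment will be recorded, and therefore each participant will provide up to two hours of audio". Appendix 2 labels the Connected Speech diagnostic hypothesis as exploratory.
- **Clock drawing and verbal fluency** (section 9.3, CoCoA-PAD Data Processing): "SHU applies machine-learning and feature extraction methods to generate derived measures". Where those models are trained is not stated.

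The protocol mentions no hold-out sample, cross-validation, optimism correction or pre-set cut-off.

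**The concern.** The Youden cut-off is the one that makes sensitivity plus specificity as large as possible in the sample at hand. Part of that maximum is real separation and part is chance. Evaluating the cut-off on the people who supplied it counts both parts as accuracy. The excess grows as groups get smaller, and the smallest group is the preclinical one, which the battery is named for.

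These figures will carry weight. Section 7.8 says that, depending on the results, "insensitive tests will be removed from the assessment to reduce time", and section 7.9 makes the device programme conditional on diagnostic accuracy being achieved. The false discovery rate adjustment in section 4.6 acts on p-values and does nothing for these estimates.

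A score produced by a classifier trained on the same participants has a related problem: if its in-sample output is used, the AUC is optimistic as well.

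**Working it through.** **The plan's own figure.** The only sizing figure for Study 1 is 90 participants (one-way ANOVA, f = 0.33, k = 3, alpha 0.05, power 0.80). With noncentrality N × f², N = 90 gives 90 × 0.1089 = 9.80 on (2, 87) degrees of freedom and power 0.793. The exact minimum is 92, and the projected 94 give 0.811. The stated figure therefore reproduces to within two participants. It concerns the ANOVA and says nothing about the precision or bias of sensitivity and specificity.

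**Inputs for the accuracy check.**
- Group sizes 36 v 18 and 36 v 40 (section 11.3).
- True AUC: an assumption. Appendix 1 quotes 0.71 for the clock-drawing reference test and 0.89 for the SILT reference test, so 0.70, 0.80 and 0.89 were used, plus 0.50 for a worthless test.
- Score model: an assumption. Normal with equal variance, controls at 0 and cases at δ = √2 × Φ⁻¹(AUC).

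**Method.** In each of 10,000 simulated samples the cut-off c maximising empirical J = sensitivity + specificity − 1 was chosen. The apparent values come from the same sample. The true values of that same cut-off in new people are sensitivity 1 − Φ(c − δ) and specificity Φ(c). Results are means.

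| Groups | True AUC | Sensitivity, apparent → true | Specificity, apparent → true | J, apparent → true | Excess J |
|---|---|---|---|---|---|
| 36 v 18 | 0.50 | 0.642 → 0.534 | 0.520 → 0.466 | 0.162 → 0.000 | 0.162 |
| 36 v 18 | 0.70 | 0.734 → 0.640 | 0.667 → 0.621 | 0.402 → 0.262 | 0.140 |
| 36 v 18 | 0.80 | 0.796 → 0.713 | 0.746 → 0.706 | 0.542 → 0.420 | 0.122 |
| 36 v 18 | 0.89 | 0.867 → 0.796 | 0.824 → 0.791 | 0.691 → 0.587 | 0.104 |
| 36 v 40 | 0.50 | 0.569 → 0.505 | 0.564 → 0.495 | 0.132 → 0.000 | 0.132 |
| 36 v 40 | 0.70 | 0.683 → 0.632 | 0.691 → 0.634 | 0.374 → 0.266 | 0.108 |
| 36 v 40 | 0.80 | 0.756 → 0.711 | 0.765 → 0.715 | 0.520 → 0.426 | 0.094 |
| 36 v 40 | 0.89 | 0.831 → 0.792 | 0.843 → 0.801 | 0.674 → 0.594 | 0.080 |

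Over AUC 0.70 to 0.89 the sensitivity excess runs from 0.734 − 0.640 = 0.094 down to 0.867 − 0.796 = 0.071 (preclinical), and from 0.051 down to 0.039 (prodromal). The specificity excess runs from 0.033 to 0.057 across both comparisons.

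The result does not depend on comparing with an imperfectly chosen cut-off. The best J any cut-off could reach is 2Φ(δ/2) − 1. At AUC 0.70, δ = √2 × 0.524 = 0.742, so the best J is 2Φ(0.371) − 1 = 0.289, and the apparent 0.402 exceeds even that by about 0.11. Appendix 1 also quotes higher reference AUCs, up to 0.97 for the COBALT reference test. The excess shrinks as AUC rises, so it would be smaller there.

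**Speech classifier, only if scored on its own training participants.** As a stand-in for a network of unstated size, a linear discriminant was fitted to pure-noise features (true AUC 0.50; 2,000 runs). Apparent AUC with 1, 3, 5 and 10 features was 0.57, 0.63, 0.68 and 0.76 for 36 v 18, and 0.55, 0.60, 0.64 and 0.71 for 36 v 40. The feature counts are assumptions.

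**The case against.** The strongest reply is that this belongs in the statistical analysis plan. Section 11.4 calls itself provisional, promises a final plan agreed with a statistician and published before data collection, and does not rule out a bootstrap. That stands in part: the final plan may add a correction. But the protocol does more than stay silent. It names the optimised values as a measure of accuracy for two primary objectives, with no outside cut-off and one sample, so following it as written gives biased figures.

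Several stronger readings are tempting, and the documents do not support them:
- **That all reported accuracy is inflated.** Choosing a Youden cut-off leaves the AUC of an unfitted subtest score untouched, and AUC is already among the named measures.
- **That clock drawing and verbal fluency are scored by models trained on these participants.** Section 9.3 does not say where those models are trained.
- **That the speech scores are certain to be in-sample.** Section 9.3 does not say whether they are in-sample or out-of-fold. It also has the classifier outcome entered into the database in one place and only derived speech features returned in another. The hypothesis is exploratory in any case. An extreme noise example with very many features would show near-perfect separation, but no feature count is given to justify it.
- **That the recording leaks the reference standard into the preclinical comparison.** The appointment includes the M-ACE (section 6.6), and nothing excludes that segment. Its use as classifier input is an inference, however. Controls and preclinical cases are both unimpaired on the M-ACE and are separated by pTau-217, so any leak would bear on prodromal v control only.
- **That the wrong subtests will be kept.** Section 7.8 does not tie removal to Youden values, a similar excess across subtests tends to preserve their average ranking, and section 7.9 foresees larger validation before clinical use.

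**Conclusion.** The point holds for sensitivity and specificity at the Youden cut-off. For a true AUC of 0.70 to 0.89, the plan as written overstates sensitivity by about 7 to 9 points in the preclinical comparison and 4 to 5 in the prodromal one, specificity by about 3 to 6 points, and J by 0.10 to 0.14 and 0.08 to 0.11. A subtest with no diagnostic value would still show an average J of 0.16 or 0.13. These sizes rest on the projected group numbers, the equal-variance binormal model and the assumed AUCs; the direction of the bias does not.

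For the exploratory speech classifier the point is conditional: it applies if its output is evaluated by ROC in the participants it was trained on. For clock drawing and verbal fluency, the protocol should first state where the models are trained.

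**What to change.** In section 11.4:
1. Make AUC with a 95% confidence interval the lead accuracy measure for each subtest.
2. Report Youden sensitivity and specificity with bootstrap or cross-validated optimism correction, re-selecting the cut-off within every resample.

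In section 9.3:
1. If the speech classifier's output is to be evaluated by ROC in these participants, enter out-of-fold predictions, or scores from a model fixed on outside data.
2. Leave the M-ACE portion of the recording out of the classifier's input, because the M-ACE helps define the prodromal group. The timestamps and task identifiers that accompany the audio should help to separate it.
3. State where the clock-drawing and verbal-fluency models are trained, and apply the out-of-fold rule to them only if it is on this sample.

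The cost is some extra analysis code and slightly lower reported sensitivity and specificity. No new data are needed. The rule on which scores are entered should be settled before the database is locked, since stored in-sample scores could not be corrected later without retraining.
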